2 INTRODUCTION

Acetyl-CoA carboxylase (ACC) is a biotin carboxylase that catalyzes the adenosine triphosphate (ATP) dependent condensation of acetyl-CoA and carbonate to form malonyl-CoA. The malonyl-CoA produced by ACC serves two major physiologic functions. It is an essential and rate-limiting substrate for de novo lipogenesis (DNL) and it acts as an allosteric inhibitor of the enzyme carnitine-palmitoyltransferase 1 (CPT-1). CPT-1 is responsible for the transport of long-chain fatty acyl-CoAs across the mitochondrial membrane into the mitochondria where they become available for fatty acid oxidation. The transport step is rate-determining for this process. Thus, ACC is positioned as a key physiologic switch regulating the transition from oxidative to lipogenic metabolism. Reducing malonyl-CoA production via ACC inhibition is expected to inhibit simultaneously the de novo synthesis of fatty acids and to increase flux through CPT-1

leading to increased β -oxidation of long-chain fatty acids. There are two closely related isoforms of ACC, ACC1, and ACC2, encoded by separate gene products that differ in tissue and cellular distribution.

PF-05221304 is a potent, selective, orally bioavailable, and reversible dual ACC1/2 inhibitor designed to have asymmetric distribution to the liver, with ≥ 100 fold asymmetric hepatic distribution demonstrated in both rats and monkeys; as such PF-05221304 is expected to inhibit DNL and stimulate fatty acid oxidation in the liver to a greater extent than in peripheral tissues. In humans, administration of PF-05221304 has been shown to suppress hepatic DNL in a Phase 1 trial in healthy subjects; in addition, the drug is expected to stimulate hepatic fatty acid oxidation, and consequently reduce fat accumulation in the liver. This inhibition of hepatic DNL is postulated to result in a decrease and normalization of the excessive DNL observed in nonalcoholic fatty liver disease (NAFLD). In addition, the inhibition of ACC via administration of PF-05221304 also has the potential for anti-inflammatory effects in nonalcoholic steatohepatitis (NASH).

The current study is the first clinical trial proposed with PF-05221304 in adult subjects with NAFLD. The investigational product will be administered orally, once-daily for up to 16 weeks. It is designed as a dose-ranging trial with placebo and 4 active doses of PF-05221304 to assess the safety, tolerability and the effect of PF-05221304 on liver fat. In addition, assessment of the effect of PF-05221304 on other pharmacodynamics/exploratory parameters is planned.

This SAP provides the detailed methodology for summary and statistical analyses of the data collected in study C1171002. This document may modify the plans outlined in the protocol; however, any major modifications of the primary endpoint definition or its analysis will also be reflected in a protocol amendment.

2.1 Study Objectives

Primary Objective:

 To evaluate the dose-response for the effect on liver fat, as assessed via MRI-PDFF, with a range of PF-05221304 doses administered daily in adults with nonalcoholic fatty liver disease (entire study population)
Secondary Objective(s):

 To evaluate the dose-response for the effect on ALT with a range of PF-05221304 doses administered daily in the 1st tier stratification comprising of adults with diagnosed/presumed nonalcoholic steatohepatitis, only To evaluate the safety and tolerability of a range of PF-05221304 doses administered daily in adults with nonalcoholic fatty liver disease (entire study population)
Tertiary Objective(s):

 To evaluate the dose-response for the effect on liver fat, over time, with a range of PF-05221304 doses administered daily in adults with nonalcoholic fatty liver disease (entire study population)

CCI	
	
 To evaluate the dose-response for the effect on key liver function tests and NASH-related biomarkers over time, with a range of PF-05221304 doses administered daily in the 1st tier stratification comprising of adults with diagnosed/presumed nonalcoholic steatohepatitis, only
CCI	
	
 To evaluate the dose-response for the effect on other potentially mechanism-related parameters and metabolic parameters, over time, with a range of PF-05221304 doses administered daily in adults with nonalcoholic fatty liver disease (entire study population)
	
 To evaluate the dose-response for the effect on glycemic parameters, over time, with a range of PF-05221304 doses administered daily in the 2nd tier stratification comprising of adults with T2DM, only
CCI	

2.2 Study Design

This is a randomized, double-blind, placebo-controlled, 5-arm (placebo, plus 4 active doses of PF-05221304), parallel-group study.

Determination of eligibility for this study will occur via a sequential, 3-step process – starting with pre-qualification. Subjects identified to be eligible based on pre-qualification will then undergo Visit 1 (Screen 1) with only those confirmed to continue to be eligible progressing to Visit 2 (Screen 2). For a given subject, this 3-step eligibility assessment (from pre-qualification to Screen 2, inclusive) may take up to 2-months.

[figure not shown]
*Once confirmed to be eligible based on Screen 2 procedure(s), subjects will progress to a run-in phase when concomitant treatment(s) will be stabilized, and baseline-related visits will occur. At Visit 5 (Day 1), subjects will be randomized to receive 1 of 5 blinded regimens for a duration of up to 16 weeks (ie, 108±4 days). Excluding the pre-qualification visit, this study includes a total of 12 scheduled outpatient visits **in the***

morning, 3 random visits for PK blood draws, **and** a potential for up to at least 3 visits for repeat assessments (for procedures/tests at Visit 1, Visit 2, or 2nd Follow-up visit). The total participation, from Visit 1 (Screen 1) to 2nd Follow-up visit, will be 27-weeks (minimum) to 35-weeks (maximum) – refer to Figure 1.

At least 360 subjects (72 per arm) will be randomized at approximately 120 sites to ensure a minimum of 300 subjects (60 per arm) complete the study. **In each arm**, ≥ 50% of subjects randomized will be deemed to be eligible for 1st tier stratification of diagnosed/presumed NASH; with the remaining subjects per arm eligible for 1st tier stratification of NAFLD with likely minimal inflammation and fibrosis (refer to Section 4.3 of the protocol for more details).

Figure 1. C1171002 Study Design

Subjects who are noted to have non-evaluable baseline MRI-PDFF, as determined by the sponsor-identified central imaging vendor, may be replaced, at sponsor discretion (refer to Section 7.1.4 of the protocol for more details); otherwise, there are no plans to replace subjects who are prematurely withdrawn. To ensure that the required minimum number of subjects complete the study, the plan is to overenroll by approximate 20% to account for premature early withdrawal.

3 ENDPOINTS AND BASELINE VARIABLES: DEFINITIONS AND CONVENTIONS

3.1 Primary Endpoint(s)

- *Percent change from baseline in liver fat, as assessed using MRI-PDFF, at Week 16 in subjects with nonalcoholic fatty liver disease (entire study population)*

3.2 Secondary Endpoint(s)

- *Percent change from baseline in ALT, at Week 16 in adults with diagnosed/presumed nonalcoholic steatohepatitis, only*
- *Assessment of TEAEs, safety-related clinical laboratory tests, vital signs, and 12-lead ECGs in adults with nonalcoholic fatty liver disease (entire study population) – refer to Section 3.4, below*

3.3 Tertiary Endpoints

- *Percent change from baseline in liver fat, as assessed using MRI-PDFF, over time up to Week 16 in adults with nonalcoholic fatty liver disease (entire study population)*

CCI [Redacted]

- *In adults with diagnosed/presumed nonalcoholic steatohepatitis only, percent change from baseline, over time up to Week 16, for:*
 - ✓ *ALT, AST, Alkaline Phosphatase (ALKP), GGT, Total Bilirubin (TBILI)*
 - ✓ *CK18-M30 and CK18-M65*
- CCI [Redacted]
- ✓ *Pro-C3 & Pro-C6*

CCI [Redacted]

[Redacted]

CCI

- *In adults with nonalcoholic fatty liver disease (entire study population), percent change from baseline, over time up to Week 16, for:*
 - Potentially mechanism-related parameters –
 - ✓ Serum apolipoprotein A1, B (total), C3, E
- *Metabolic parameters*
 - ✓ Fasting lipid panel (fasting total cholesterol, direct LDL-C, HDL-C, triglycerides, VLDL)
- Change from baseline (**not percent change from baseline as mentioned in protocol**), over time up to Week 16 for Glycated hemoglobin (HbA1c)

CCI

- *In adults with T2DM, only*
 - Change from baseline, over time up to Week 16 for
 - ✓ Glycated hemoglobin (HbA1c)
 - ✓ Fasting plasma glucose (FPG)
 - ✓ Fasting plasma insulin (FPI)
 - ✓ HOMA-IR

CCI

3.4.2 Laboratory Data

For the specific laboratory parameters listed in Table 2 below, the following endpoints will be evaluated using CaPS:

- Absolute value and change from baseline at week 2, week 4, week 6, week 8, week 12, week 16, and Follow-up.
- Number of occurrences of these abnormalities defined as “Flag Level” or “Alert Level”
- Number of subjects with these abnormalities defined as “Flag Level” or “Alert Level”

Parameter	Flag Level	Alert Level	Conventional Units
Fasting Serum Triglycerides	≥ 400	≥ 600	mg/dL
	--	≥ 800	mg/dL
Platelet Count	< 100	< 75	$x 10^3$ /mm³
Fasting Plasma Glucose	< 70	≤ 49	mg/dL
	≥ 140	>270	mg/dL
Alanine aminotransferase	$\geq 2x$ ULN	Pfizer std flag for PCC	IU/L
Aspartate aminotransferase	$\geq 2x$ ULN	Pfizer std flag for PCC	IU/L

Alkaline Phosphatase	$\geq 2x$ ULN	Pfizer std flag for PCC	IU/L
Gamma Glutamyl Transferase	$> ULN$	Pfizer std flag for PCC	IU/L
Total Bilirubin	$> 1.5x$ ULN	Pfizer std flag for PCC	mg/dL
Direct (Conjugated) Bilirubin	$> ULN$	Pfizer std flag for PCC	mg/dL

*All flag level changes are cumulative from baseline (defined as result closest prior to dosing at Visit 5 (Day 1)); reflect either threshold for entry criteria into study or clinically significant thresholds

^All alert changes are cumulative from baseline (defined as result closest prior to dosing at Visit 5 (Day 1); values when noted during the study, by central laboratory necessitates rapid notification (via fax/e-mail) to site and Study Clinician

PCC – potential clinical concern

ULN – upper limit of normal as determined by the central laboratory

The safety events of special clinical concern as defined in Table 2 will be summarized and the frequency of laboratory abnormalities (both number of occurrence **and** number of subjects).

Across all the laboratory-related analytes (for safety and pharmacodynamics/biomarker), inclusion of results when assessed at scheduled nominal visits meet the following criteria:-

1. Collection must be prior to AM dose of double-blinded study medication
2. Collection permitted to be *nonfasted for the following analytes and will be permitted to be grouped with fasted results* given that nonfasted state is not known to impact results

Chemistry panel	Hematology	Other	Urinalysis
Total bilirubin	Hemoglobin	aPTT	pH
Direct bilirubin	Hematocrit	PT	Protein
Indirect bilirubin	RBC	INR	Glucose
Alk Phos	MCV	Urine-drug-testing	Ketones
ALT	MCH	Serology testing	Bilirubin
AST	MCHC	[hepatitis B,	Urobilinogen
GGT	WBC	hepatitis C, HIV]	Blood
Urea Nitrogen	Neutrophils (abs)	Alpha-1-antitrypsin	Nitrite
Creatinine	Lymphocytes (abs)	Ceruloplasmin	Leukocyte esterase
Uric acid	Monocytes (abs)	HbA1C	Microscopic UA
Calcium	Eosinophils (abs)	CCI	
Total protein	Basophils (abs)	β -hCG	
Albumin	Platelets	FSH	
Creatine kinase	Reticulocyte count%		
Sodium	Reticulocyte count		
Potassium			
Bicarbonate			
Chloride			

3. ***But***, the following analytes will only be included in summary outputs if collections are confirmed to be following an overnight fast of at least 8 hours as it is well known that fasting status impacts numerical results (***or*** there is insufficient data regarding effect of meals on results)

Biomarkers	Lipid-related	Other Blood-related
-------------------	----------------------	----------------------------

CCI Plasma Glucose Plasma Insulin CCI CK18-M30 CK18-M65 ProC3 ProC6	Total cholesterol HDL-C Direct LDL-C Triglycerides VLDL Apolipoprotein A1 Apolipoprotein B Apolipoprotein C3 Apolipoprotein E	CCI
--	---	-----

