**Table 4. All Planned Safety-Related Laboratory Tests and Exploratory Biomarkers in Study C1171002**

Hematology	Chemistry	Urinalysis	Other
-Hemoglobin -Hematocrit -RBC count -Reticulocyte count (Abs) -MCV -MCH -MCHC -Platelet count -WBC count -Total neutrophils (Abs) -Eosinophils (Abs) -Monocytes (Abs) -Basophils (Abs) -Lymphocytes (Abs)	-BUN -Creatinine [ and eGFR using MDRD] - Plasma glucose (fasting) -Calcium -Sodium -Potassium -Chloride -Total CO 2 (Bicarbonate) -AST (SGOT) -ALT (SGPT) -Alkaline phosphatase -GGT -Total Bilirubin -Direct (conjugated) bilirubin a -Indirect (unconjugated) bilirubin a -Total bile acids -Creatine Kinase b -Uric acid -Albumin -Total protein	-pH -Glucose (qual) -Protein (qual) -Blood (qual) -Ketones -Nitrites -Leukocyte esterase -Urobilinogen -Urine bilirubin -Microscopy c	-Plasma aPTT, PT, INR -Serum FSH d -Serum and urine pregnancy test [refer to Section 7.3.1] -Urine drug test e -Serology f : HBsAg, HBcAb, HCVAb (and if positive, reflex HCV RNA), HIV -α1-antitrypsin f -Ceruleplasmin f -Serum % carbohydrate deficient transferrin f -HbA1C g -Fasting Lipid Panel h
Additional Tests (Needed for instances of suspected Hy's law)		Additional exploratory biomarker assessmentsi include: -Serum apolipoproteins A1, B(total), C3, E CCI [REDACTED] -Plasma Insulin (fasting) -Calculate HOMA-IR using fasting glucose & insulin CCI [REDACTED] -CK18-M30, CK18-M65 -ProC3 & ProC6 CCI [REDACTED]	
-AST, ALT -Total bilirubin -Albumin -Alkaline phosphatase -Direct bilirubin -Indirect bilirubin -Creatine kinase -GGT -PT/INR -Total bile acids -Acetaminophen drug levels and/or protein adduct level			

- Direct + indirect bilirubin measured at Pre-qualification, Screen 1, V4, and V5; after initiation of investigational product, direct + indirect bilirubin measured only when total bilirubin is >ULN
- Test to be assessed at Pre-qualification, Screen 1, V4, and V5; after initiation of investigational product, this test measured only when ALT or AST is >ULN
- Only if urine dipstick is positive for blood, protein, nitrites or leukocyte esterase
- At Pre-qualification, Screen 1, ONLY; and in females, only

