7.2 Interim Analyses and Summaries

For planned interim analysis and for triggered unblinded reviews, IRC members will receive the following data summarized/analyzed by randomized arm along with the relevant subject data listings.

Study conduct and subject characteristics:

- Study conduct issues (e.g., enrollment status, currentness of the database, time between randomization and first treatment, eligibility violations)
- Subject evaluation groups
- Subject stratification factors
- Demographic and other baseline characteristics

Safety Data:

The Committee will monitor certain specific safety-related laboratory parameters, vital sign parameters, and treatment-emergent adverse events (TEAEs) as well as serious adverse events (SAEs including death) listings in an unblinded manner for overall

frequency of occurrence of events. To do so, here are the listings which should be provided:

- TEAEs (and SAEs) leading to temporary discontinuation of dosing in subjects;
- TEAEs (and SAEs) leading to permanent discontinuation and withdrawal of subjects;
- The listing of individual subject-level TEAEs and SAEs;
- All instances of hypoglycemia, or hyperglycemia, or platelet reduction, or hypertriglyceridemia leading to permanent withdrawal;
- Listing of Treatment emergent adverse events (TEAEs) under the 3-tier approach as defined in section 6.6 of this SAP;
- Listings of SAEs/deaths and narratives requested from the safety database (ie, ARGUS or similar)

CCI [REDACTED] laboratory parameters outlined in Table 2 of this SAP represent the minimum list of parameters which will be listed and provided to the committee. This list may be expanded depending on team blinded review.

The Committee will receive the distribution of subjects over time whose values cross the boundaries (ie Flag and Alert levels separately) for each of the parameters included in Table 2 of this SAP.

Percent change from baseline in other fasting lipid parameters including total cholesterol, direct low density lipoprotein cholesterol (LDL-C), very low density lipoprotein (VLDL) and high density lipoprotein cholesterol (HDL-C) will be also provided for review.

The following graphical representations of the parameters in Table 2, CCI [REDACTED] other fasting lipid parameters (see list above) will be provided:

- Individual values: median response with Q1 and Q3 per randomized arm over time, Box and whiskers plots as depicted in Appendix 3.2,

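### After dosing starts, direct bilirubin is measured only when total bilirubin exceeds ULN, so its planned by-visit summaries rest on a result-selected subset and are biased upward in expectation

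*SAP*

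**What the plan says.** SAP 3.4.2 opens its list of laboratory endpoints with "For the specific laboratory parameters listed in Table 2 below, the following endpoints will be evaluated using CaPS". The first endpoint is "Absolute value and change from baseline at week 2, week 4, week 6, week 8, week 12, week 16, and Follow-up"; the others are numbers of occurrences and numbers of subjects at flag or alert level. One of the Table 2 rows is "Direct (Conjugated) Bilirubin", with a flag above ULN. The section adds: "The safety events of special clinical concern as defined in Table 2 will be summarized and the frequency of laboratory abnormalities". SAP 6.6.1 confirms descriptive statistics for these endpoints.

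SAP 7.2 carries the same list into the IRC package. It plans "The following graphical representations of the parameters in Table 2": medians with quartiles, and box plots, by arm over time, for values, changes and percent changes.

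The protocol's footnote to Table 4 sets a different collection scheme for this analyte. Before dosing: "Direct + indirect bilirubin measured at Pre-qualification, Screen 1, V4, and V5". Afterwards: "after initiation of investigational product, direct + indirect bilirubin measured only when total bilirubin is >ULN".

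**The concern.** Baseline is available for everyone, because SAP 3.5 takes it from Visit 5 or, failing that, Visit 4, and both are scheduled direct-bilirubin visits. Every later result exists only because a correlated analyte was high in the same sample. A table or plot of value by visit then compares an all-comers baseline with a selected follow-up group. Change from baseline compares a selected follow-up value with an unselected baseline in the same person. Both are pushed upward with no drug effect.

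The SAP has no visible rule for this. Where it sets out "inclusion of results when assessed at scheduled nominal visits meet the following criteria", the criteria concern timing before the dose and fasting status, and direct bilirubin is listed as an ordinary chemistry analyte. SAP 5.3 refers missing safety data to sponsor standard rules that are not shown.

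What is at stake is whether this output can be read at all. SAP 7.2 says that no formal statistical analysis is done on safety data at the interim, so the IRC works from listings and plots, and Protocol 9.5 allows the interim results to be used for stopping a dose level. Arms would be compared on subsets formed after randomization. If a dose changed how often total bilirubin exceeds ULN, it would also change who is tested.

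**Working it through.** **1. The two texts side by side**

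| Time | Who has direct bilirubin (Protocol Table 4) | What the SAP summarises |
|---|---|---|
| Visits 4 and 5 | Everyone | Baseline |
| Weeks 2, 4, 6, 8, 12, 16 and Follow-up | Only if total bilirubin is above ULN | Value and change; for the IRC also percent change and plots |

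The documents give no bilirubin mean, SD, share above ULN or expected number tested. There is no planned figure to reproduce, and any size rests on assumptions.

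**2. Direction of the bias**

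Let t and d be centred log total and log direct bilirubin at a post-dose visit, d₀ log direct at baseline, and ρ the within-subject correlation of t. Assume d = 0.7·t + a stable personal term + noise. With no drug effect,

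E[d − d₀ | t] = 0.7·(1 − ρ)·t,

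which is positive for the high t that triggers the test, for any ρ below 1. Example with 5% above ULN, SD of t 0.40 and ρ = 0.7:

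- E[t | t > ULN] = 0.40 × 0.1031 / 0.05 = 0.825, where 0.1031 is the normal density at 1.645;
- 0.7 × 0.3 × 0.825 = 0.173, and exp(0.173) − 1 = +18.9%.

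**3. Size over a range**

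The same model was simulated with 2,000,000 subjects per scenario, no drug effect and no time trend. Assumptions, none from the documents: log-SD of total bilirubin 0.40; personal term SD 0.2; visit noise SD 0.1; direct ULN at the 98th percentile of direct. The entry limits of Protocol 4.1, criterion 6 (total below 1.5 × ULN, direct not above ULN) were applied at one screening visit. The arm size of 72 is from Protocol 9.1. Change is the ratio of mean follow-up to mean baseline, minus 1, among those measured.

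| Share above ULN | ρ | Measured per 72 | Arm-visit empty | Change in those measured | Arm-visit mean change above 0, if not empty |
|---|---|---|---|---|---|
| 2% | 0.5 | 1.3 | 28% | +38.6% | 92% |
| 2% | 0.7 | 1.2 | 31% | +23.0% | 86% |
| 2% | 0.9 | 1.0 | 36% | +8.1% | 69% |
| 5% | 0.5 | 3.3 | 4% | +32.0% | 95% |
| 5% | 0.7 | 3.1 | 4% | +19.0% | 88% |
| 5% | 0.9 | 2.8 | 6% | +6.5% | 72% |
| 10% | 0.5 | 6.7 | 0% | +26.3% | 97% |
| 10% | 0.7 | 6.3 | 0% | +15.9% | 92% |
| 10% | 0.9 | 5.9 | 0% | +5.4% | 75% |

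The 5%, ρ = 0.7 row (+19.0%) agrees with the hand calculation. With everyone measured, the change is 0.0% in all nine scenarios. The mean value of those measured lies 52% to 87% above the all-subject baseline mean.

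**4. At the planned interim**

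About 120 subjects through Week 6 is 120 / 5 = 24 per arm if evenly split. The measured share in the simulation runs from 1.4% to 9.2%, so 0.014 × 24 = 0.3 to 0.092 × 24 = 2.2 subjects would stand behind one arm's box at one visit.

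**5. Flag counts**

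Direct bilirubin above ULN with total at or below ULN is not measured after dosing, so the count can only be too low. The simulated share missed is 17% to 68%, but this depends heavily on the assumed link between direct and total. If direct were a fixed fraction of total and the two limits stood in the same ratio, nothing would be missed.

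**The case against.** A reader might infer that every arm will show a false rise. The documents do not support that. A given arm-visit may be empty or flat: under the assumptions above, the chance that all five arms show a positive mean change at a visit, given that each has data, is 16% to 86% (0.69⁵ to 0.97⁵). Subjects with stably raised bilirubin, such as those with Gilbert syndrome whom inclusion criterion 6 allows, would be tested repeatedly against their own raised baseline and add little change. The simulation has no such subgroup, though its ρ = 0.9 rows point the same way. The upward bias is an expectation.

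A reader might also infer an inflated rate of flagged results. SAP 3.4.2 plans counts of occurrences and subjects, not a percentage of those tested, and the counts err downward.

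The strongest counter-argument concerns consequences, and it stands. The potential-DILI criteria in Protocol 8.4.2 use AST or ALT with total bilirubin. Total bilirubin is itself in SAP Table 2, is measured at every on-site visit, and is analysed by MMRM in the NASH stratum. The triggers for unblinded IRC review in Protocol 3.3 do not involve direct bilirubin. The IRC also receives listings of the Table 2 parameters and could see how few results there are. The sponsor's standards, which are not shown, may already deal with reflex tests.

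None of this makes the by-visit output interpretable. Seeing a small n reveals sparsity but does not remove selection, and the visible SAP text asks for the output without restriction.

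**Conclusion.** The two current texts do not fit together. As written, SAP 3.4.2 and 7.2 call for by-visit values, changes and plots of an analyte that after dosing exists only where total bilirubin is above ULN. These outputs rest on a result-selected subset of unknown size and are biased upward in expectation in each arm. With 2% to 10% of subjects above ULN and within-subject correlation 0.5 to 0.9, about 1 to 7 of 72 subjects per arm-visit are measured, and their mean change is +5% to +39% with no true change. The direction needs only that direct and total bilirubin are positively correlated and vary within subjects. The size depends on the assumed distribution.

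A reader might go further and conclude that liver-safety monitoring is compromised. It is not: total bilirubin and the transaminases carry that signal, and both are measured throughout. The damage is confined to the interpretability of this output and to incomplete flag counts.

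**What to change.** In SAP 3.4.2 and 7.2:

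- remove direct bilirubin from the by-visit value, change, percent-change and plot outputs, and keep total bilirubin as the by-visit parameter;
- report per arm the number of subjects tested for direct bilirubin after dosing, and the number with total and direct both above ULN at any post-dose time, with all treated subjects as denominator;
- add a listing of each direct result with its paired total bilirubin.

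The combined count suits an all-treated denominator because total bilirubin is measured at each visit and direct follows whenever total is above ULN.

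The standard laboratory tables follow sponsor rules that are not shown. If they would otherwise summarise indirect bilirubin, or creatine kinase (measured after dosing only when ALT or AST is above ULN), by visit, the same rule should apply.

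The cost is SAP wording and the loss of one by-visit output. No new samples and no protocol change are needed. Direct bilirubin above ULN with normal total remains unmeasured, and a footnote should say so.

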8. In those ***without*** biopsy-proven NASH, ***only***, at Pre-Qualification ***and*** Visit 1 (Screen 1), meet the following criteria **for liver stiffness**, based on assessment via FibroScan®, with a single repeat permitted to assess eligibility, if needed, at each of these 2 visits:
  - LSM  $\geq$  7.0 kPa – classified as presumed NASH;
  - LSM  $<$  7.0 kPa – classified as NAFLD with likely minimal inflammation and fibrosis;
  - ***NOTE***: if Pre-Qualification and Visit 1 values are discordant in stratifying a given subject, 1 more assessment via FibroScan® on ***a separate day*** is permitted, with 2 of the 4 assessments (at least 1 between pre-qualification and repeat pre-qualification, ***plus*** at least 1 between Screen 1 and repeat Screen 1) required to meet above threshold ***before progressing*** to Screen 2.
9. In those ***without*** biopsy-proven NASH, ***only***, at Pre-Qualification ***and*** Visit 1 (Screen 1), meet the following criteria, as assessed by the sponsor-identified central laboratory, with a single repeat permitted to assess eligibility, if needed, at each of these 2 visits:
  - ALT  $>$  ULN and  $\leq$  5x ULN – classified as presumed NASH;
  - ALT  $\leq$  1.25x ULN – classified as NAFLD with likely minimal inflammation and fibrosis;
  - ***NOTE***: if Pre-Qualification and Visit 1 values are discordant in stratifying a given subject, 1 more blood collection on ***a separate day*** is permitted, with 2 of the 4 assessments (at least 1 between pre-qualification and repeat pre-qualification, ***plus*** at least 1 between Screen 1 and repeat Screen 1) required to meet above threshold ***before progressing*** to Screen 2.
10. In those ***without*** biopsy-proven NASH, ***only***, at Pre-Qualification ***and*** Visit 1 (Screen 1), meet  $\geq$  2 of the following 5 criteria for metabolic syndrome [***for laboratory parameters***, results must be as assessed by the sponsor-identified central laboratory, with a single repeat permitted to assess eligibility, if needed, at each of these 2 visits]:
  - FPG  $\geq$  100 mg/dL (5.6 mmol/L), ***or*** on pharmacological agents ***with explicit purpose*** of improving glycemic control (refer to [Section 5.8.1](#) for acceptable versus prohibited medications);

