  - Preexisting AST or ALT baseline values above the normal range: AST or ALT values > 2 times the baseline values *and* > 3x ULN *or* >8x ULN (whichever is smaller).
  - Preexisting values of TBili above the normal range: TBili level increased from baseline value by an amount of at least > ULN *or* if the value reaches >3x ULN (whichever is smaller).

Rises in AST/ALT and TBili separated by more than a few weeks should be assessed individually based on clinical judgment; any case where uncertainty remains as to whether it represents a potential Hy's law case should be reviewed with the sponsor.

The subject should return to the investigator site and be evaluated as soon as possible, preferably **within 48 hours** from awareness of the abnormal results. This evaluation should include laboratory tests, detailed history, and physical assessment.

In addition to repeating measurements of AST and ALT and TBili, laboratory tests should include albumin, creatine kinase (CK), direct and indirect bilirubin, gamma-glutamyl transferase (GGT), prothrombin time (PT)/international normalized ratio (INR), total bile acids, alkaline phosphatase and acetaminophen drug and/or protein adduct levels – refer to [Table 4](#). Consideration should also be given to drawing a separate tube of clotted blood and an anticoagulated tube of blood for further testing, as needed, for further contemporaneous analyses at the time of the recognized initial abnormalities to determine etiology. A detailed history, including relevant information, such as review of ethanol, acetaminophen (either by itself or as a coformulated product in prescription or over-the-counter medications), recreational drug, supplement (herbal) use and consumption, family history, sexual history, travel history, history of contact with a jaundiced person, surgery, blood transfusion, history of liver or allergic disease, and potential occupational exposure to chemicals, should be collected. Further testing for acute hepatitis A, B, C, D, and E infection and liver imaging (eg, biliary tract) may be warranted.

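### The ALT, AST and high-glucose flags in SAP Table 2 lie inside the entry range and are counted without a stated baseline condition, so by-arm flag counts mix pre-existing with new elevations

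*SAP*

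**What the plan says.** SAP 3.4.2 names three outputs for each Table 2 parameter: "Absolute value and change from baseline at week 2, week 4, week 6, week 8, week 12, week 16, and Follow-up", the number of flagged occurrences, and the "Number of subjects with these abnormalities defined as" Flag Level or Alert Level. For ALT and AST the Flag Level is 2x ULN or above. For GGT it is above ULN, and for high fasting glucose 140 mg/dL or above. The Alert Level for the liver tests is given only as "Pfizer std flag for PCC".

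The Table 2 footnote reads "All flag level changes are cumulative from baseline (defined as result closest prior to dosing at Visit 5 (Day 1", with a parallel sentence for alerts. SAP 7.2 then gives the IRC the "distribution of subjects over time whose values cross the boundaries (ie Flag and Alert levels separately" for every Table 2 parameter.

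On entry, Protocol 4.1 criterion 9 admits subjects without biopsy-proven NASH at ALT above ULN and up to "5x ULN – classified as presumed NASH". Criterion 6 admits fasting glucose up to 270 mg/dL. The visible criteria set no ALT cap for biopsy-proven NASH and no AST or GGT limit. At least half of each arm is to be diagnosed or presumed NASH (SAP 2.2).

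Protocol 8.4.2 treats raised baselines differently. For potential drug-induced liver injury (DILI) it uses "Preexisting AST or ALT baseline values above the normal range: AST or ALT values > 2 times the baseline values", together with further ULN limits and a bilirubin criterion.

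**The concern.** A count of subjects past a threshold is a safety signal only to the extent that subjects start below it. Here a presumed NASH subject entering at 2x to 5x ULN meets the ALT flag before the first dose.

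Randomization seeks balance within the 1st tier (Protocol 4.3), so entry status alone mainly adds noise between arms. The direction comes from the drug. Protocol 1.3.1 anticipates a fall in ALT in this stratum. That fall takes pre-existing elevations out of the active-arm count, and new elevations can replace them without the total exceeding placebo. A reader of the by-arm table, or of the IRC display, could then take a lower count as reassurance when it is partly an efficacy result.

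**Working it through.** The plan states no expected flag count, so there is no figure to reproduce. The nearest stated ALT figure is the power claim in Protocol 9.1: a 35% difference, SD 55%, 30 per arm, one-sided 10%. It gives 35 / (55 × √(2/30)) = 2.465; 2.465 − 1.282 = 1.183; power 88%, consistent with the stated 80% or more. It is used here only as the source of the 35% fall.

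**Step 1. Flag against entry limit.**

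| Parameter | Flag (SAP Table 2) | Entry limit (Protocol 4.1) | Flag inside entry range? |
|---|---|---|---|
| Triglycerides | ≥ 400 mg/dL | ≤ 400 mg/dL | Only at the edge |
| Total bilirubin | > 1.5x ULN | < 1.5x ULN (Gilbert exception) | No, exception aside |
| Direct bilirubin | > ULN | ≤ ULN | No |
| ALT | ≥ 2x ULN | up to 5x ULN, presumed NASH | Yes |
| AST | ≥ 2x ULN | none visible | Yes |
| GGT | > ULN | none visible | Yes |
| Glucose (high) | ≥ 140 mg/dL | ≤ 270 mg/dL | Yes |

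**Step 2. The footnote.** SAP Table 3 (vital signs) carries the same flag footnote, but where a baseline-relative flag is intended its cells say so (rises of 30 and 20 mm Hg from baseline). The ALT and AST cells contain only a multiple of ULN, and the SAP does not say what the footnote does to such a cell.

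**Step 3. The protocol's own baseline-adjusted rule.** In ULN units the ALT component of 8.4.2 is the smaller of 8 and max(2 × baseline, 3). Baselines of 2, 3, 4 and 5 give thresholds of 4, 6, 8 and 8. No subject with baseline at or below 5x ULN meets it on entry value alone, whereas every one of those four baselines meets the SAP flag.

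**Step 4. Share past the flag at entry (assumed distribution).** The documents give no baseline ALT distribution. Assume log-normal ALT truncated to 1–5x ULN, with pre-truncation median m of 1.2 to 2.2x ULN and log-SD s of 0.40 or 0.55:

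share = [Φ((ln 5 − ln m)/s) − Φ((ln 2 − ln m)/s)] / [Φ((ln 5 − ln m)/s) − Φ((0 − ln m)/s)]

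- m = 1.2, s = 0.40: 0.1006 / 0.6755 = 0.15
- m = 2.2, s = 0.40: 0.574 / 0.956 = 0.60

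A log-uniform baseline on 1–5x ULN gives ln 2.5 / ln 5 = 0.57, near the top of this range.

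**Step 5. Effect on the Week 16 count (simulated).** Take 36 such subjects per arm (half of 72) and within-subject log-SD 0.2, with no change on placebo and a uniform 35% fall on drug. In the last column, 4 of the 36 drug subjects also have ALT triple from the lowered level, to 0.65 × 3 = 1.95 times baseline.

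| m, s | At flag at entry | Placebo | Drug | Drug with 4 new rises |
|---|---|---|---|---|
| 1.2, 0.40 | 5.3 | 6.7 | 0.9 | 4.3 |
| 1.2, 0.55 | 9.9 | 10.8 | 2.8 | 6.1 |
| 1.5, 0.40 | 10.0 | 11.0 | 2.2 | 5.7 |
| 1.5, 0.55 | 13.6 | 14.2 | 4.6 | 7.7 |
| 1.8, 0.40 | 15.2 | 15.7 | 4.3 | 7.6 |
| 1.8, 0.55 | 17.1 | 17.3 | 6.5 | 9.5 |
| 2.2, 0.40 | 21.6 | 21.3 | 7.8 | 10.8 |
| 2.2, 0.55 | 21.1 | 20.9 | 9.1 | 11.9 |

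In every row the drug arm with four new rises still shows fewer flags than placebo. No such calculation was made for AST, GGT or glucose.

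**The case against.** Four arguments carry weight.

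- **The text may already condition on baseline.** The footnote may be meant to, and in SAP 7.2 values that cross a boundary could mean incident crossings. Laboratory summaries follow sponsor standards (SAP 6.6.1) that are not shown, and parts of SAP 6.6.2 and Appendix 2.3 are blacked out. This stands as an ambiguity: no visible text settles it, and one sentence would.
- **The Alert Level is unseen.** It refers to a sponsor standard whose values and baseline rule are not in the documents. The point is therefore limited to the Flag Level.
- **Other outputs show new rises.** SAP 3.4.2 evaluates change from baseline at each visit. The IRC receives subject listings, change and percent-change box plots by arm with outliers drawn, and TEAE and SAE listings. Potential DILI cases are reported as SAEs. This stands, with limits: the DILI route also needs a bilirubin criterion, and none of the visible displays counts subjects by baseline status.
- **The illustration is favourable to the point.** It applies the 35% fall to everyone and looks at one visit at full effect. A subject flagged early, before ALT falls, still counts as ever flagged, so that gap would be smaller. It places all 36 subjects above ULN, although Protocol 1.3.2 notes that many biopsy-diagnosed patients have ALT at or below ULN. It also treats screening limits as baseline limits, although baseline follows a run-in of at least 6 weeks.

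Two stronger readings are tempting. A reader might infer that the plan as a whole would hide liver injury; the outputs above do not support that. A reader might also infer that the flag table decides whether a dose is stopped. The documents do not say so: IRC decision criteria sit in a charter (Protocol 9.5), and the stated triggers for extra unblinded review are adverse-event and discontinuation percentages (Protocol 3.3).

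**Conclusion.** The point holds for the flag counts in SAP 3.4.2 and their IRC display in 7.2. As visibly written, they combine elevations present at entry with elevations arising on treatment, and an ALT-lowering drug shifts the mix in its own favour. This is more than missing detail: SAP 3.4.1 already counts adverse events only when new or worsened, and Protocol 8.4.2 already scales ALT and AST to a raised baseline.

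The size is uncertain because baseline ALT is unknown. Under the assumed distributions about 15% to 60% of presumed NASH subjects, or 5 to 22 of 36 per arm, are past the ALT flag before dosing. Expected Week 16 flags are then about 7 to 21 on placebo and 1 to 9 on drug, rising to 4 to 12 on drug if four subjects have new rises. These figures illustrate direction and do not predict the trial. For AST, GGT and glucose the same structure is present but its size was not estimated.

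**What to change.** In SAP 3.4.2 and 7.2:

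1. Report ALT, AST, GGT and glucose flags by arm separately for subjects below the flag at baseline (treatment-emergent) and subjects at or above it.
2. For the second group, add a shift table or a table of maximum multiple of baseline, by 1st-tier stratum for the liver tests. A shift table cut only at the flag would miss a move from 2x to 5x ULN, so it needs finer categories.
3. Add by-arm counts of subjects meeting the ALT/AST component of the baseline-relative definition already in Protocol 8.4.2, labelled as the transaminase component only. The new rises in Step 5 centre on 1.95 times baseline, just under that multiple, so this count complements item 2 and does not replace it.
4. Define what the cumulative-from-baseline footnote means for a fixed threshold. State whether the sponsor standard behind the Alert Level conditions on baseline.

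The cost is SAP wording and programming. No data collection, clinical threshold or management rule changes. If sponsor standards already split by baseline, item 1 reduces to a sentence saying so.
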